9.7	Case Report Forms and Study Records	59
9.8	Protocol Violations/Deviations.....	60
9.9	Access to Source Documentation	60
9.10	Data Generation and Analysis	60
9.11	Financial Disclosure.....	60
9.12	Publication and Disclosure Policy	60
10	REFERENCES	61

LIST OF IN-TEXT TABLES

Table 1	Study Drug Starting Dose Information	36
Table 2	Dose Titration Plan	37
Table 3	List of Laboratory Tests.....	42
Table 4	Maximum Annual Blood Volumes Required	43
Table 5	Adverse Event Severity.....	45

LIST OF APPENDICES

Appendix 1	Schedule of Events.....	64
Appendix 2	Definition of Childbearing Potential and Contraceptive Requirements	66
Appendix 3	Approval and Signature Page: Principal Investigator	68

LIST OF ABBREVIATIONS AND DEFINITIONS OF TERMS

ACTH	adrenocorticotrophic hormone
ADA	anti-drug antibodies
AE	adverse event
AGHD	adult growth hormone deficiency
ALB	Albumin
ALT	alanine aminotransferase (SGPT)
ALP	alkaline phosphatase
ALS	acid labile subunit
ANCOVA	analysis of covariance
AST	aspartate aminotransferase (SGOT)
AUC	area under curve
BMI	body mass index
BUN	blood urea nitrogen
CA	Calcium
CFR	Code of Federal Regulations
CI	confidence interval
CM	concomitant medications
C _{max}	maximum plasma concentration
CRA	clinical research associate
CRF	case report form
CRO	contract research organization
CSR	clinical study report
CTCAE V.4.0	Common Terminology Criteria for Adverse Events Version 4.0
CV	coefficient of variation
DP	drug product
DSMB	data and safety monitoring board
eCRF	electronic case report form
ECG	electrocardiogram

FDA	Food and Drug Administration
FPG	fasting plasma glucose
GCP	Good Clinical Practice
GGT	gamma glutamyl transferase
GHD	growth hormone deficiency
GHR	growth hormone receptor
GHRH	growth hormone releasing hormone
GLP	Good Laboratory Practice
HbA1c	glycated hemoglobin
HBV	hepatitis B virus
HCV	hepatitis C virus
Hct	hematocrit
Hgb	hemoglobin
hGH	human growth hormone
HIV	human immuno-deficiency virus
HT-SDS	height standard deviation score
Hs-CRP	highly sensitivity C-reactive protein
ICH	International Conference on Harmonisation
ICF	informed consent form
IEC	independent ethics committee
IGF-I	insulin-like growth factor-I
IGF-I SDS Reference Range	IGF-I SDS range of -2.00 to 2.00
IGF-I Mean SDS Target Range	Protocol designated IGF-I SDS range of 0 to 1.50
IGF-I SDS Therapeutic Range	IGF-I SDS range of -1.50 to 1.50
IGF-I SDS	insulin-like growth factor-I standard deviation score
IGFBP-3	insulin-like growth factor-binding protein 3
IND	Investigational New Drug
IRB	Institutional Review Board

ITT	Intention to Treat
IWRS	Interactive Web Response System
K	Potassium
kDa	kilodalton
kg	Kilogram
LDL	low density lipoprotein
LDH	lactic dehydrogenase
LS	least squares
MAPK	mitogen-activated protein kinase
MCH	mean corpuscular hemoglobin
MCHC	mean corpuscular hemoglobin concentration
MCV	mean corpuscular volume
MedDRA	Medical Dictionary for Regulatory Activities
mg	Milligram
mITT	modified intention To Treat
MW	molecular weight
Na	Sodium
NOAEL	no observed adverse effect level
NYHA	New York Heart Association
PD	pharmacodynamics
PGHD	pediatric growth hormone deficiency
PI	principal investigator
PI3K	phosphoinositide-3 kinase
PK	pharmacokinetic
r	correlation coefficient
RBC	red blood cell (count)
rhGH	recombinant human growth hormone
SAE	serious adverse event
SC	subcutaneous

SD	standard deviation
SDS	standard deviation score
SE	standard error
SGOT	serum glutamic oxaloacetic transaminase (AST)
SGPT	serum glutamic pyruvic transaminase (ALT)
SOP	standard operating procedure
SRC	safety review committee
STAT	signal transducer and activator of transcription
SUSAR	suspected, unexpected serious adverse reaction
$t_{1/2}$	terminal elimination half life
T4	Thyroxine
TEAE	treatment emergent adverse event
T_{max}	time to maximum plasma concentration
TSH	thyroid stimulating hormone
US	United States
WBC	white blood cell (count)
WHO	World Health Organization
WHODDE	WHO Drug Dictionary Enhanced
μg	microgram

Rationale for the Proposed Changes to Protocol 15VR8

The main objectives of this protocol revision (Version 2) are to introduce modifications to the starting doses, dose frequency, continued dosing in rollover subjects, and dose titration plan used in the study. Somavaratan is being investigated as a once-monthly SC injection in adults with GHD in a Phase 2 study (Protocol 15VR7), where one of the objectives is the assessment of the starting dose and the dose titration plan. This open label extension study (Protocol 15VR8) is open to any subjects that complete a Versartis somavaratan study, as well as up to 40 new adult subjects with GHD.

At an initial starting dose of 0.6 to 1.0 mg/kg in the Phase 2 study, IGF-I levels 7 days after the first dose were > 2.0 SDS in 19/36 subjects (53%) and > 3.0 SDS in 14/36 subjects (39%). These IGF-I values were transient and not accompanied by clinically important adverse events.

Despite dose adjustments (reductions), of the 29 subjects that completed 5 doses in the Phase 2 study at the time of this protocol amendment, IGF-I values 7 days after the last (fifth) dose were > 2.0 SDS in 16 subjects (55%) and > 3.0 SDS in 7 subjects (24%).

Based on these findings, it was determined that:

- A lower starting dose is needed
- The maintenance doses in rollover subjects seems to be too high, and a lower maintenance dose is needed
- The dose titration plan was not adequate to address the high IGF-I levels at Day 8 and a new titration plan based solely on IGF-I SDS 7 days after dosing is proposed
- The dosing frequency should be revised to twice-monthly to allow for adequate response during the dosing interval with reduced IGF-I excursions above 2.0 SDS
- Dosing initiation and titration should be made on a fixed (mg) basis and not be based upon-body weight adjusted (mg/kg) basis

Starting Dose

Evaluation of the doses resulting in Day 8 IGF-I above and below 2.0 SDS indicate that for adult subjects with GHD (except women receiving estrogens), 20 mg was the lowest dose that did not result in a response > 2.0 SDS in 90% of the subjects. For women receiving estrogens, a similar analysis was performed and the identified starting dose was 40 mg.

A fixed starting dose regardless of weight, age and gender is therefore planned for this study:

- 20 mg for all subjects other than women receiving oral estrogen
- 40 mg for women receiving oral estrogen

Dosing Frequency

Data from the ongoing analysis of the Phase 2 study have shown that the pre-dose (trough) IGF-I levels were similar to the baseline IGF-I levels (prior to any somavaratan exposure), suggesting that the duration of effect was less than one month. In addition, after the last (fifth) dose of somavaratan in the Phase 2 study, IGF-I levels at 21 days after dosing had already diminished to values not different than the pre-dose levels. Based on this analysis, the planned dosing frequency for this study is:

- Twice-Monthly

Continued Dosing in Rollover Subjects Presently Participating in This Study

As previously described, approximately 50% of the subjects who completed the 15VR7 study and rolled over to the 15VR8 protocol still have high IGF-I levels 7 days after somavaratan administration (Day 8). A lower dose is needed to prevent the transient IGF-I excursions. For rollover subjects, it is proposed that the current once monthly dose they are receiving will be divided in 2, and rounded down to the nearest even number (minimum dose 20 mg, 40 mg for women on oral estrogen) and administered twice-monthly (example: current dose is 54 mg, divided by two = 27 mg, rounded down to nearest even number = 26 mg. The subject will begin to receive somavaratan 26 mg twice-monthly).

Titration Plan

The titration plan will be modified to be based exclusively on IGF-I at Day 8, which represents the sampling point of the highest response to Somavaratan. The objective of the new titration plan is to achieve an IGF-I at Day 8 within 0 and 2.0 SDS while ensuring that the IGF-I response does not exceed 2.0 SDS.

After subjects achieve maintenance dosing (two consecutive IGF-I at Day 8 within target range under the same dose) doses may be modified based on the Investigator or Medical Monitor clinical judgment with the goal to maintain IGF-I SDS at Day 8 within target range (0 to 2.0).

Summary of the Proposed Changes to Version 2 of Protocol 15VR8

Synopsis

- Updated Objective section to include as a secondary objective to evaluate the dose (starting and maintenance) and the dose titration plan of twice-monthly somavaratan during long-term treatment
- Updated **Study Design** section to describe the twice-monthly dosing regimen, starting doses and treatment cohorts
- Updated the **Inclusion/Exclusion Criteria** to indicate that new naïve to somavaratan treatment subjects must agree to a wash out period of minimum 14 days and have a screening IGF-I SDS < 0
- Updated the **Test Product, Dose and Mode of Administration** section indicating the new dosing regimen and dose titration for all subjects based on the Day 8 IGF-I SDS. Updated the Dose Titration Plan (Table 2)

Updated Section 3.1, **Overall Study Design and Plan** to describe:

- The twice-monthly dosing regimen and starting doses that will be used for all subjects
- The visit schedule all subjects will follow
- The dosing cohorts that will be used in the study
- The Dose Titration Plan (Table 2)

Updated Section 3.7, **Inclusion Criteria**:

- **Criterion # 2** describes the eligible subjects that may enroll in the study
- **Criterion # 3** describes the requirement that new naïve to somavaratan subjects entering the study must have a screening IGF-I SDS < 0
- **Criterion # 7 describes the requirement that new naïve to somavaratan subjects** currently receiving daily rhGH injections for treatment of GHD, must agree to stop taking prescribed daily rhGH therapy for the washout period of ≥ 14 days

Updated Section 4, **Study Treatments**:

- This section has been revised to describe the starting doses, dose titration plan, introduction of the somavaratan autoinjector device, treatment groups, and dose schedule for all subjects

Updated Section 6, **Study Activities**:

- This section has been updated to describe the activities for all subjects that will occur during Screening and in the first month of treatment as well as during the monthly dose titration

Updated **Appendix 1, Schedule of Events**:

- Appendix 1 revised to describe the activities for all subjects enrolled in the study

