STUDY DESIGN General This open-label extension study will evaluate the safety of long-term twice-monthly administration of somavaratan in adults with GHD. This is an open-label, multicenter study open to subjects completing a Versartis adult GHD study as well as approximately 40 new somavaratan naïve subjects (either rhGH treatment naïve or currently receiving daily rhGH therapy). All subjects will receive twice-monthly (every 15 days \pm 2 days) subcutaneous (SC) somavaratan. Doses will be titrated to each subject's individual IGF-I responses based on the IGF-I level 7 days post-dose until a maintenance dose is achieved. Maintenance dose is defined as an IGF-I value between 0 and 2.0 SDS for two consecutive 7 day post-dose time points (Day 8, peak level). Subjects receiving somavaratan once-monthly in this study (Protocol 15VR8) or in a previous somavaratan study (Protocol 15VR7), will have their dose decreased by half (minimum dose of 20 mg, 40 mg for women on estrogen, rounded down to the nearest even number) and will be titrated per the Dose Titration Plan (Table 2). New subjects enrolling in this study will be assigned to one of two cohorts and will receive a starting dose of 20 mg twice-monthly (40 mg for women on estrogen) (Table 1) and will be

titrated per the Dose Titration Plan (Table 2). Maintenance doses may be adjusted further based on PD data at the discretion of the Investigator or Medical Monitor.

Table 1 Study Drug Starting Dose Information:

Subject Cohort Assignment	Fixed Starting Study Dose	Frequency of Administration
Cohort 1: Adults with GHD irrespective of age and gender	20 mg	Twice-Monthly
Cohort 2: Women receiving oral estrogens	40 mg	Twice-Monthly

Table 2 Dose Titration Plan

Downward Dose Titration		
IGF-I at Day 8	Cohort 1	Cohort 2
0 to 2.0 SDS	No change in dosing	No change in dosing
2.01 to 3.0 SDS	4 mg dose decrement	4 mg dose decrement
Greater than 3.0 SDS	10 mg dose decrement	10 mg dose decrement
Upward Dose Titration ¹		
IGF-I at Day 8	Cohort 1	Cohort 2
-1.0 to 0 SDS	4 mg dose increment	10 mg dose increment
Less than -1.0 to -2.0 SDS	10 mg dose increment	20 mg dose increment
Less than -2.0 SDS	20 mg dose increment	40 mg dose increment

1: Maximum allowable dose is 250.0 mg

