Study in clinic visits/blood sample collections will occur every week for the first 4 weeks of the study, followed by monthly in clinic visits until the subject has reached maintenance dosing. Some of the blood sample collections may be obtained in the subject's home throughout the study. Somavaratan doses will be administered in clinic During Month 1 and at each monthly Day 1 visit until maintenance dosing is achieved. After Month 1, Day 16 doses may be administered at home. In clinic visits will occur quarterly during the first year. Although quarterly visits will continue throughout the study, after the first year blood samples will be collected every 6 months, with intervening visits used for brief physical exams and collection of AEs and concomitant medications.

A total of up to 250 subjects will be enrolled.

Safety

Subjects will be monitored for safety throughout their participation in the study. Safety will be monitored by physical examination, inspection of injection sites, vital signs, ECGs (new subjects only), and clinical laboratory determinations. Adverse events (AEs) and concomitant medications (CMs) will be captured. AEs will be graded using the Common Terminology Criteria for Adverse Events (CTCAE). AEs will be coded using the MedDRA dictionary and CMs using the WHO Drug Dictionary (WHODDE, WHO Drug Dictionary Enhanced).

For new subjects, electrocardiograms (12-lead ECGs, triplicate tracings) will be conducted at Screening and repeated at Day 1 and Month 4 at 3 days (± 1 day) after dosing.

An external data safety and monitoring board (DSMB) will monitor and protect the safety of the study subjects throughout the study duration. DSMB meetings will occur twice yearly (approximately every 6 months).

The Stopping Criteria for individual subjects include:

1. The Principal Investigator (PI) and/or Medical Monitor conclude it is unsafe or not in the subject's best interest to continue.
2. IGF-I SDS ≥ 3.0 SDS on two consecutive Day 8 time points despite dose adjustments.
3. IGF-I SDS ≥ 2.0 SDS on two consecutive Day 8 time points despite dose adjustments and accompanied by clinically meaningful drug-related AEs, as determined by the Investigator and the Medical Monitor.

Subjects meeting individual stopping criteria will be withdrawn from the study.

The Stopping Criteria for the study itself include the determination that the study is unsafe to continue.

Pharmacokinetics (PK) and Pharmacodynamics (PD)

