3 INVESTIGATIONAL PLAN

3.1 Overall Study Design and Plan

This open-label extension study will evaluate the safety of long-term twice-monthly administration of somavaratan in adults with GHD. This study is open to subjects completing a Versartis adult GHD study as well as approximately 40 new somavaratan naïve subjects (either rhGH treatment naïve or currently receiving daily rhGH therapy). A total of up to 250 subjects may be enrolled in this study. All subjects will receive twice-monthly (every 15 days \pm 2 days) subcutaneous (SC) somavaratan. All subjects will have somavaratan doses titrated per the Dose Titration Plan (Table 2) to each subject's individual IGF-I responses based on the IGF-I level collected 7 days post-dose (Day 8) until a maintenance dose is achieved. Maintenance dose is defined as an IGF-I value between 0 and 2.0 SDS for two consecutive 7 day post-dose time points (peak).

Subjects receiving somavaratan once-monthly in this study (Protocol 15VR8) or in a previous somavaratan study (Protocol 15VR7), will have their dose decreased by half (minimum dose of 20 mg, 40 mg for women on estrogen, rounded down the nearest even number) and will be titrated per the Dose Titration Plan (Table 2).

New subjects naïve to somavaratan treatment enrolling in this study will be assigned to one of two cohorts and will receive a starting dose of 20 mg twice-monthly (40 mg for women on estrogen) (Table 1) and will be titrated per the Dose Titration Plan (Table 2).

Maintenance doses may be adjusted further at the discretion of the Investigator or Medical Monitor while maintaining IGF-I at Day 8 (7 days post dose) within target range. For patients on maintenance dose that have IGF-I levels $>$ 2.0 SDS at any point during the maintenance period, dose adjustment shall be made by the Investigator or Medical Monitor based on clinical judgment with the objective to achieve and maintain IGF-I at day 7 post-dose between 0 and 2.0 SDS. Any change in somavaratan dose in a subject that has achieved maintenance dosing will be followed by an ad-hoc Day 8 IGF-I measurement to ensure IGF-I values are within target range (0 and 2.0 SDS).

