For new subjects, treatment is initiated at the fixed starting dose (20 mg or 40 mg, as per assigned cohort), with subsequent doses determined based on individual IGF-I response. IGF-I levels (ng/mL) will be checked at pre-dose (trough) and at 7 (± 1) days after dosing (Day 8, peak) until dose stabilization is achieved. The 7 day post-dose (Day 8, peak) IGF-I SDS value will be used to determine dose adjustments with a target range of 0 to 2.0 SDS. If the peak IGF-I SDS is below the target range (e.g., < 0 SDS), the dose shall be titrated up according to the Dose Titration Plan (Table 2). If the peak IGF-I SDS is above the target range (e.g., > 2.0 SDS), the dose shall be titrated down according to the Dose Titration Plan (Table 2). Once a subject has achieved an IGF-I SDS within the target range for two consecutive months, s/he will be considered dose stabilized and will continue to receive that maintenance dose for the remainder of the study unless further adjustment becomes necessary. After dose stabilization is achieved, IGF-I levels will no longer be tested monthly; maintenance subjects will have pre-dose and 7 days post-dose IGF-I levels drawn every 3 months for the first year, and then every 6 months thereafter. If a subject on maintenance dose has an IGF-I value outside the target range, further dose adjustments will be considered on an individual basis by the Investigator or Medical Monitor with the objective to achieve and maintain IGF-I SDS at Day 8 within target range

(IGF-I SDS 0 - 2.0). Any change in somavaratan dose in a subject that has achieved maintenance dosing will be followed by an ad-hoc Day 8 IGF-I measurement to ensure IGF-I values are within target range (0 and 2.0 SDS).

Subjects will be monitored for safety throughout their participation in the study. Safety will be monitored by physical examination, inspection of injection sites, vital signs, , clinical laboratory determinations (including complete blood count, chemistry, lipid profile, urinalysis, measurements of adrenal function, thyroid function, and glucose metabolism), ECG's (new subjects only), and immunogenicity assessments. Immunogenicity assessments will include anti-drug antibodies (ADA). All ADA positive samples will be characterized in an *in vitro* cell assay that determines if the serum sample can inhibit human growth hormone (hGH)-stimulated cell proliferation.

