4.2 Treatments Administered

All subjects will receive somavaratan twice-monthly.

- Subjects receiving somavaratan once monthly in a prior Versartis adult GHD study or in this study, irrespective of the cohort assignment and whether they have achieved maintenance dosing, will transition to receive treatment at half of their current dose (rounded down to the nearest even number, minimum dose of 20 mg).
- New subjects naïve to somavaratan will be assigned to one of two treatment cohorts (Table 1) with different starting doses based on the subject's use of oral estrogens. The initial dose will be a fixed dose.

All subjects will have Day 8 IGF-I SDS evaluated each month with subsequent dose adjustments made per the Dose Titration Plan (Table 2).

Table 1 Study Drug Starting Dose Information

Subject Cohort Assignment	Fixed Starting Study Dose	Frequency of Administration
Cohort 1: Adults with GHD irrespective of age and gender	20 mg	Twice-Monthly ¹
Cohort 2: Women receiving oral estrogens	40 mg	Twice-Monthly ¹

1: Allowable dosing window is every 15 days ± 2 days

Table 2 Dose Titration Plan

Downward Dose Titration		
IGF-I at Day 8	Cohort 1	Cohort 2
0 to 2.0 SDS	No change in dosing	No change in dosing
2.01 to 3.0 SDS	4 mg dose decrement	4 mg dose decrement
Greater than 3.0 SDS	10 mg dose decrement	10 mg dose decrement
Upward Dose Titration¹		
IGF-I at Day 8	Cohort 1	Cohort 2
-1.0 to 0 SDS	4 mg dose increment	10 mg dose increment
-1.0 to -2.0 SDS	10 mg dose increment	20 mg dose increment
Less than -2.0 SDS	20 mg dose increment	40 mg dose increment

1: Maximum allowable dose is 250.0 mg

The starting doses and Dose Titration Plan (Tables 1 and 2) may be altered by the Sponsor based on continued evaluation of the Phase 2 data and/or data gathered during this study. Adjustments may be implemented to alleviate safety concerns or optimize normalization of IGF-I SDS responses. The Investigator and Medical Monitor may agree to temporarily alter or suspend a subject's dose during illness or injury.

If a subject on maintenance dose has an IGF-I value outside the target range, further dose adjustments will be considered on an individual basis by the Investigator or Medical Monitor with the objective to achieve and maintain IGF-I SDS at Day 8 within target range (IGF-I SDS between 0 - 2.0)

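### Table 2's dosing bands overlap at their boundaries, and the titration objective has no stated count of subjects in range

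*Combined protocol and SAP*

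**What the plan says.** **Target and maintenance.** Section 3.1 says that the Day 8 value "will be used to determine dose adjustments with a target range of 0 to 2.0 SDS". Doses go up below 0 and down above 2.0. Maintenance requires two consecutive Day 8 values from 0 to 2.0.

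**Table 2.** The titration table appears twice in the Synopsis and once in Section 4.2. In all three copies the no-change row runs from 0 to 2.0, the first decrement row is "2.01 to 3.0 SDS", and the first increment row runs from -1.0 to 0. For the second increment row the Synopsis has "Less than -1.0 to -2.0 SDS". Section 4.2 drops the opening two words, so that row starts at -1.0 itself.

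**Stopping criterion 3** (Synopsis and Section 3.5.1) begins with "IGF-I SDS ≥ 2.0 SDS on two consecutive Day 8 time points despite dose adjustments". It also requires clinically meaningful drug-related adverse events, as judged by the Investigator and the Medical Monitor.

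**Definitions list.** The entry for the IGF-I mean SDS target range reads "Protocol designated IGF-I SDS range of 0 to 1.50".

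**Analysis.** Sections 2.2 and 8.4 make evaluation of the starting dose, maintenance dose and titration plan a secondary objective. The only analysis sentence in Section 8.4 concerns antibodies. Section 8.1 gives continuous variables n, mean, SD, median, minimum and maximum, and gives categorical variables n and percentage. The Synopsis promises a summary of response to dosing but does not define response.

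**The concern.** A titration table is a decision rule, so each Day 8 value should lead to exactly one action. As written, a reading of 0 counts toward maintenance and also sits in an increment row. A reading of -1.0 leads to different doses depending on which copy or row a site uses. A reading of 2.0 is in range and also satisfies the IGF-I part of a withdrawal rule.

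The same bands are the natural yardstick for the dose and titration objective. The rationale for Version 2 rests on the proportions of Phase 2 subjects above 2.0 and 3.0 SDS, and the new plan aims to hold each subject's Day 8 value within 0 to 2.0. If only default continuous summaries are produced, the report will not show directly whether those proportions fell.

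**Working it through.** **1. Boundary values under each rule**

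| Day 8 SDS | Table 2, Synopsis copies | Table 2, Section 4.2 copy | Other rules |
|---|---|---|---|
| 0 | no change, or +4 mg (Cohort 1) / +10 mg (Cohort 2) | same overlap | Section 3.1 raises the dose only below 0; 0 counts toward maintenance |
| -1.0 | +4 mg (Cohort 1) / +10 mg (Cohort 2) | +4 or +10 mg (Cohort 1); +10 or +20 mg (Cohort 2) | none |
| 1.51 to 1.99 | no change | no change | outside the definitions-list range only |
| 2.0 | no change | no change | counts toward maintenance; meets the IGF-I part of criterion 3 |
| 2.01 | 4 mg decrement | 4 mg decrement | meets the IGF-I part of criterion 3 |

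Relative to the starting doses, the ambiguity at 0 is 4/20 = 20% in Cohort 1 and 10/40 = 25% in Cohort 2.

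The overlap at 2.0 can matter as follows. A reading of 2.01 draws a 4 mg decrement, and the next reading is 2.0. The subject is back in range, yet two consecutive values at or above 2.0 have followed a dose adjustment. With a qualifying adverse event, criterion 3 is met.

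**2. How often a boundary value occurs**

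The documents give no Day 8 distribution for the new regimen, so I assume normality with mean m and SD s. The chance of a reading reported as exactly b is Φ((b + h - m)/s) - Φ((b - h - m)/s), with h = 0.005 for two decimals and h = 0.05 for one.

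For b = 2.0, with m from 0.5 to 2.0 and s from 0.8 to 1.6:
- two decimals: 0.0009 to 0.0050, about 0.1% to 0.5%
- one decimal: 0.0086 to 0.0498, about 1% to 5%

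Only the distance from b to m enters the formula, here 0 to 1.5. The same ranges therefore hold for b = 0 with m from 0 to 1.5, and for b = -1.0 with m from -1.0 to 0.5.

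If all 250 subjects were measured at one time point, the expected number per boundary is 250 × 0.0009 = 0.2 to 250 × 0.0050 = 1.25 readings at two decimals. At one decimal it is 250 × 0.0086 = 2.2 to 250 × 0.0498 = 12.5.

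**3. The proportions behind Version 2**

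The stated percentages reproduce. After the first dose, 19/36 = 52.8% were above 2.0 and 14/36 = 38.9% above 3.0. After the fifth, 16/29 = 55.2% and 7/29 = 24.1%. These are counts of subjects by band.

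**4. What the default summaries show**

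Take a mean of exactly 1.0, mid-target. Under normality the in-range share is Φ(1/s) - Φ(-1/s):
- s = 0.8: 78.9%
- s = 1.2: 59.5%
- s = 1.6: 46.8%

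An on-target mean is thus compatible with very different in-range shares. The SD helps only if a distribution is assumed, and titrated values need not be normal. The minimum and maximum show whether anyone is out of range, not how many. The SD values are illustrative and not a forecast.

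**The case against.** The strongest reply is that the working rules are nearly consistent and the rest is tidying. Much of this stands. Section 3.1 raises doses only below 0, which points to no change at 0. Both Synopsis copies put -1.0 in the smaller increment, so the Section 4.2 row looks like two dropped words. Table 2's limit of 2.01 suggests two-decimal reporting, the rarer case. However, Section 4.2 holds the copy that the list of in-text tables points to, and a site should not need to compare sections to find a dose.

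A reader might infer that two target ranges compete. The documents do not support that. The 1.50 limit appears only in the definitions list, is labelled a mean range, and triggers no titration, maintenance or stopping action. Over the grid in step 2, about 8% to 23% of readings fall between 1.5 and 2.0, but no rule treats them differently.

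A reader might also take 2.0 to be a stopping value in itself. It is not: criterion 3 needs two consecutive values, persistence despite dose adjustments, and drug-related adverse events. Withdrawing an in-range subject with such events is not contradictory, and criterion 1 already permits it.

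On reporting, Section 8.1 calls itself a brief summary and defers detail to a statistical analysis plan. It allows n and percentage for categorical variables, and Section 8.7 permits periodic review of the dosing regimen. Such a plan could contain the table. Nothing in the available text commits to it.

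**Conclusion.** The point holds in two limited parts.

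First, Table 2 gives two actions at 0 in every copy and at -1.0 in Section 4.2, and criterion 3 overlaps the in-range limit at 2.0. The frequency is low: about 0.1% to 0.5% of readings per boundary at two decimals, 1% to 5% at one, given the assumed normal distributions. The case for correction is that these are dosing and stopping rules, not that many subjects are affected. The 0 to 1.50 entry is a leftover.

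Second, the dose and titration objective has no stated analysis beyond default continuous summaries and an undefined promise to summarise response. The per-subject shares that motivated Version 2 are not among the stated outputs.

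It would go too far to say that the same Day 8 result can be both success and excursion. The protocol defines no success endpoint, and it describes excursions as above 2.0. Nor does the point touch the primary safety objective.

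**What to change.** **Thresholds.** In every copy of Table 2, use these rows:
- 0 to 2.0: no change
- -1.0 to < 0: first increment
- less than -1.0 to -2.0: second increment
- less than -2.0: third increment

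The decrement rows can stay. Set criterion 3 to > 2.0 in the Synopsis and Section 3.5.1; criterion 1 still covers an in-range subject with adverse events. Delete the definitions-list entry or correct it to 0 to 2.0.

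**Reporting.** In Section 8.4, add the number and percentage of subjects below 0, from 0 to 2.0, above 2.0 and above 3.0 SDS at each Day 8 time point, and the percentage reaching maintenance. State that the above-3.0 group is part of the above-2.0 group. Keep the mean and SD alongside.

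**Cost.** Small text edits and one descriptive table from data already collected. The in-range percentage may look less favourable than the mean.
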